Subcutaneous administration of RZL-012 (50 mg/mL) to farm pigs resulted in mild increases in neutrophils in both sexes at the 24 hour post-dose collection, which were most typical of an inflammatory response. Increases in neutrophils had resolved by the Day 14 collection.

Analysis of the plasma samples following subcutaneous administration of RZL-012 (Group 4) found that both female and male farm pigs were exposed to RZL-012. Mean systemic exposure (area under the concentration versus time curve between zero and the 24 hour timepoint [AUC0-24hr]) and maximum observed concentration (Cmax) values, were 3700 (hr\*ng/mL) and 529 (ng/mL), respectively, for males and mean systemic exposure (AUC0-24hr) and Cmax values, were 2940 (hr\*ng/mL) and 528 (ng/mL), respectively, for females.

Upon evaluation of the injection site photographs, no irritation was observed but transient redness was noted. Upon microscopic evaluation at 24 hours and 14 days, test article related findings in the injected subcutaneous tissue was noted. These findings were characterized by necrosis of the subcutaneous fat and muscle accompanied by acute inflammation at 24 hours post-dose. At 14 days, residual necrotic tissue in the injected areas was noted with evidence of on-going healing characterized by chronic inflammation and fibrosis. There was no evidence of systemic toxicity at 24 hours or 14 Days

The 14 day interim results of this study demonstrated that administration of 5.68 to 7.14 mg/kg to males and 5.32 to 6.33 mg/kg to females of RZL-012 (test article) over 20 injection sites in the pig was associated with expected changes in subcutaneous fat temperatures, transient changes in neutrophils, and marked localized irritation and tissue necrosis. The increase in subcutaneous fat temperature was considered to be related to the mechanism of action of RZL 012, and an indication of the efficacy of the test article. The microscopic changes noted at 24 hours were beginning to resolve at 14 days. The results of the final time point at 84 days will allow for assessment of the resolution of these findings.

Based upon the interim results of the study a NOAEL of 7.14 mg/kg in males and 6.33 mg/kg in females of RZL-012 has been established in the swine. The establishment of the NOAEL was based upon the microscopic effects being limited to the subcutaneous tissue with no systemic effects and the evidence of on-going healing at 14 days.

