Although not statistical significant, a decrease in TC and FFA blood levels was evident in subjects of the RZL-012 treated group in cohort 3. This may imply to the mode of action of RZL-012 as stimulation of a thermogenic tissue such as BAT, is known to cause a systemic

effect via the mobilization of glucose and FFA from the blood stream to feed the ongoing local thermogenesis. Thus, lipolysis of WAT triacylglycerols (TAG) stores is accelerated and the uptake of FA derived from blood-born lipoproteins is increased due to the action of lipoprotein lipase (LPL). Raziel assumes that circulating FFA utilization by the RZL-012-induced thermogenic tissue resulted in lower levels of FFA in the blood, a process that may be beneficial for health. There was no consistent pattern to suggest a connection between inflammation markers and cytokines levels and changes in thermogenic activity reflecting the intended effect of the drug as opposed to local inflammation and distinguish between events related to M1 and M2 macrophages. Though, an increase in Adiponectin blood level was evident at Day 21 and Day 28 in 3 of 6 subjects treated with RZL-012, but not in controls. Adiponectin was found to be an obligatory mediator of cold-induced browning of WAT (8). Adiponectin can be elevated under various conditions, including those that trigger tissue remodeling in favor of thermogenesis such as chronic cold exposure. Although we do not know what triggered elevation of adiponectin in this study, it is known that downstream effects of adiponectin can promote the type of tissue remodeling we are expecting.

Raziel concludes that the potential risk-benefit balance for RZL-012 is favorable, and that it is likely that higher doses of RZL-012 will generate better results. This will be assessed in the next clinical trial

Methods and results of this exploratory study are described in the Investigator's Brochure.

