#### 4. STUDY ENDPOINTS

## 4.1. PRIMARY ENDPOINTS

Safety: The main objective is the evaluation of the overall safety of RZL-012 injection into the subcutaneous fat. Therefore, the primary endpoint will be the incidence of intolerable side effects and all adverse events of RZL-012 injection into the subcutaneous fat. The dose escalation scheme will be stopped if at any dose cohort, 2 patients will experience intolerable side effects.

Efficacy: The primary endpoint for efficacy is a significant thermogenesis at the injected site compared with the contra-lateral, non-injected site. This was monitored by sensitive ( $\pm$  0.1 °C) Infra-Red thermal camera. A thermogenic effect is defined by an increase of 1 °C in the injected site when compared to the surroundings and/or the non-injected site, apparent at least 28 days after injection and non-related to inflammatory response as determined by inflammatory cytokines. The primary efficacy evaluation will be supported by results from secondary endpoints, including MRI, biopsy and biomarkers.

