#### 6.1.10. Draize Score

Subjects' skin irritancy will be evaluated by Draize score at screening Day 1 (performed 28 through 7 days prior to baseline) in order to establish a baseline to compare following drug injection.

Additional skin irritancy evaluation to assess subject's safety will be performed at baseline visit prior to injection, and on  $2h \pm 30$ min following injection, on the following day  $24h \pm 2h$  after drug injection and on study visits Day 7, 14, 21, and 28. For the 1st and 2nd cohorts if by visit Day 56 Draize score is not 0 for erythema and edema, then subject will continue to be followed every 28 days till Draize score is 0. If Draize score is 0 for erythema and edema, then subjects of these cohorts will be followed for additional 2 months (every 28 days) by phone for adverse events. For the 3rd and 4th cohorts (or the highest dose achieved) Draize score will be assessed every 28 days during the follow-up period.

Skin irritancy observations in the injected sites and contra-lateral sites will be scored using the Draize scale for scoring skin reaction:

Erythema and eschar formation		Edema formation				
No erythema	0	No edema	0			
Very slight erythema (barely perceptible)	1	Very slight edema (barely perceptible)	1			
Well defined erythema		Slight edema (edges are well defined by definite raising)	2			
Moderate to severe erythema	3	Moderate edema (raised approximately 1mm)	3			
Severe erythema (beet redness) to slight eschar formation (injuries in depth)	4	Severe edema (raised more than 1mm extending beyond area of exposure)	4			

- Total possible erythema score = 4
- Total possible edema score = 4

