#### 7.2. SAFETY MEASUREMENTS

Simple measures may help avoid specific AEs associated with the use of the RZL-012 investigational product. Thus, study subjects must be informed of possible AEs that occurred in animal studies (rats and pigs):

- Any injection site reaction may occur. Pain, swelling, itching, edema, erythema, hematoma etc.
- Slight transient injection site bleeding following injection may occur.
- Itching in the injected area may occur, and study subjects should be advised to use an antihistamine gel for topical use according to drug recommendations, wear wide cotton shirts, prevent touch with irritable clothing, avoid scratching and avoid exposure to direct sun. Itching is expected till 7 days following drug injection.
- Local erythema in the injected area.
- Local heat in the injection area.
- Study restrictions regarding concomitant medications are listed in Section 7.1.
- The local subcutaneous fat reduction may appear as a slight dip in the skin surface. This decline may be temporary and transient.
- Transient increase (72%) in the WBC count by 24 hours following injection, which returned to basal level after 14 days. Probably associated with the inflammatory response at the site of injection and involve neutrophils, monocytes and eosinophils.
- Increased level of BUN and of creatinine and minimal single cell necrosis was observed in tubular epithelium at cortico medullary junction of kidney in rats receiving a dose higher 25 times the highest dose in this study. All abnormalities were found to be reversible by Day 14.
- Increased AST level which is most typical of myofiber injury associated with study related procedures. This elevation was found to be reversible by Day 14.
- Transient increase of serum CRP levels (in rats) which returned to the basic level by 14 days.
- Marked irritancy in the injected subcutaneous tissue resulting in coagulation necrosis of relatively large areas in the subcutaneous tissue planes acutely. Necrosis persisted for up to 14 days and was accompanied by early evidence of healing in the form of chronic inflammation and fibrosis.

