- Local inflammation (minimal to moderate) with muscle degeneration, epidermal/dermal necrosis (minimal to severe) and parakeratosis (minimal). Inflammation observed at injection site was also extended to adjacent subcutaneous adipose tissue. By 56 days the inflammation was minimal, muscle degeneration was not evident and inflammation to adjacent subcutaneous adipose tissue was present.
- A slight elevation in body temperatures was noted in male pigs.
- Sinus tachycardia (in pigs), occurring at the 4 hour interval post dosing.
- In addition, other acceptable treatment to relieve drug-related AE's should be used at Investigator's discretion.

Study subjects must be informed of possible AEs that occurred in clinical studies (phase 0):

- At the injection site -local and transient: erythema, oedema, pruritus, anesthesia, pain, mass (subcutaneous scar).
- Abdominal abscess

26 May 2017 58 CONFIDENTIAL

• Transient moderate to severe elevation of the liver enzymes: Alanine aminotransferase (ALT) and Aspartate aminotransferase (AST).

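### The primary endpoint requires heat unrelated to inflammation, but the responder analysis applies no inflammation condition and never sets net-delta against the same-visit Draize scores

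*Protocol*

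**What the plan says.** **Endpoint.** Protocol synopsis, 4.1 and 10.2.2, and SAP 5.3.5, define the thermogenic effect as a 1 °C rise that is also "non-related to inflammatory response as determined by inflammatory cytokines".

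**Analysis.** Protocol 6.1.17.1.2 restates the effect as a 1 °C change from baseline in the treated-minus-untreated difference (net-delta) and drops the inflammation clause. Protocol 10.5.5 and the SAP (the second paragraph numbered 5.8.4, under Efficacy Analysis) count active-arm subjects with net-delta of at least 1. No inflammation condition appears there.

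**Panel.** Protocol 6.1.8.4 lists twelve blood markers, CRP among them, drawn in cohorts 2 to 4 on Day -1 and Days 7, 14, 21 and 28. Protocol 6.1.17.2.6 gives no numerical threshold for a change and presents the panel as evidence on mechanism of action.

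**Phase 0.** Protocol 1.2.4 (Results) reports: "There was no consistent pattern to suggest a connection between inflammation markers and cytokines levels and changes in thermogenic activity". The sentence continues: "reflecting the intended effect of the drug as opposed to local inflammation and distinguish between events related to M1 and M2 macrophages".

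**Draize.** Protocol 6.1.10 states: "Skin irritancy observations in the injected sites and contra-lateral sites will be scored using the Draize scale". Erythema and edema are each scored 0 to 4. The analysis tabulates them as safety data (Protocol 10.5.7; SAP Table 14.3.2-24) and lists them by subject (Listing 16.2.8-15). They also decide the form of later follow-up in cohorts 1 and 2.

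**The concern.** Inflammation makes skin warm, and the protocol treats this as a live possibility. Section 7.2 lists local heat and erythema among the possible reactions. In pigs (1.2.2.1.2) treated sites were warmer from Day 4-5, a period that lies between acute inflammation at 24 hours and chronic inflammation at Day 14. In phase 0 the heat was mostly seen at Day 14 or 21.

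The endpoint text recognises the problem, but the analysis does not act on it. A subject whose injected side is warm and visibly red or swollen is counted in the same way as one whose skin is clear. The vehicle arm does not correct for this, because 1.2.2.1.2 and 7.2 attribute the tissue reaction to the test article. Any resulting bias favours RZL-012. At stake is the trial's central efficacy statement, that the heat is thermogenesis and not a local reaction to an irritant injection.

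**Working it through.** The plan gives no figure to reproduce on this point. The check traces the definition, counts coverage and compares the animal findings.

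**1. Is the inflammation clause applied?** It is in the endpoint text (4.1, 10.2.2, SAP 5.3.5). It is absent from 6.1.17.1.2, from 10.5.5 and from the SAP responder paragraph. Cytokine changes are tabulated separately and no step joins them to net-delta.

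**2. Coverage of the checks.** Inputs: 32 subjects in four cohorts of 8; thermal imaging on Days 7, 14, 21, 28 and 56 in all cohorts (6.1.12; Day 1 is left out here); cytokines in cohorts 2 to 4, that is 24 subjects, on Days 7, 14, 21 and 28.

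- Imaging: 32 × 5 = 160 planned subject-visits.
- Cytokines: 24 × 4 = 96, and 96/160 = 60%.
- Day 28 alone: 24/32 = 75%. Day 56: 0/32.
- Cohort 1: none. Days 56 to 168, when duration of effect is assessed: none.
- Draize, Days 7 to 28: 32 × 4 = 128. Adding cohorts 3 and 4 at Day 56 gives 128 + 16 = 144 clearly scheduled. Cohorts 1 and 2 at Day 56 are only implied by 6.1.10; with them the total is 160.

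**3. Do blood markers follow the tissue?**

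| Source | Blood | Tissue |
|---|---|---|
| Pigs, 1.2.2.1.2 | "Increases in neutrophils had resolved by the Day 14 collection" | Day 14: "evidence of on-going healing characterized by chronic inflammation and fibrosis" |
| Rats, 7.2 | "Transient increase of serum CRP levels (in rats) which returned to the basic level by 14 days" | no paired rat tissue result at Day 14 is given |
| Species not stated, 7.2 | none paired | Day 56: inflammation minimal, yet "inflammation to adjacent subcutaneous adipose tissue was present" |

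The pig row is the only stated same-species pair, and neutrophils are not in the panel. CRP is the only panel marker for which a return to baseline in animals is reported. No animal cytokine data are given. This is reason to doubt the panel, not proof that it fails.

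**4. Illustration of size.** Assumption: a share p of active sites reaches net-delta of at least 1 through inflammation alone. The documents give no value for p, so a range is shown for one active group of 6.

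- P(at least 1 of 6) = 1 − (1 − p)^6
- P(at least 2 of 6) = 1 − (1 − p)^6 − 6p(1 − p)^5

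| p | at least 1 | at least 2 |
|---|---|---|
| 5% | 26.5% | 3.3% |
| 10% | 46.9% | 11.4% |
| 20% | 73.8% | 34.5% |
| 30% | 88.2% | 58.0% |

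Each such subject moves the cohort's responder rate by 1/6 = 16.7 percentage points.

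**5. What can Draize add?** It is local, scored on both sides, and coincides with imaging on Days 1, 7, 14, 21 and 28, including the Day 28 endpoint visit. It sees only the skin. In pigs, site photographs showed no irritation beyond transient redness, although microscopy found necrosis and inflammation in the injected fat.

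**The case against.** The strongest reply is that the evidence against the panel is thin. The animal findings mix species, and the pig blood marker is not a panel member. The Day 56 tissue inflammation is called minimal. The quoted half of the phase 0 sentence can even be read as reassurance that the heat was not inflammatory, and its detail is in an Investigator's Brochure that is not available here. All of that stands. A reader might infer that the panel has been shown to fail; the documents do not go so far. Still, a missing association with systemic markers cannot by itself exclude local inflammation.

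A reader might also infer that normal plasma results would let inflamed sites through. They would not, because the analysis uses no such gate: inflamed sites count because no condition is applied at all.

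Third, a skin score may mislead in both directions. The pig photographs show that skin can look nearly clean over inflamed fat, and the increased vascularization expected from the drug (Protocol 1.1.1) could cause faint erythema in a true responder. This stands, and it limits Draize to a supportive role.

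Fourth, Draize and thermal results are both listed by subject, so a reader could match them by hand, and the Day 56 biopsy looks at the tissue directly. Both are true. But an unplanned match leaves the primary claim to post hoc reading. The biopsy covers three cohort 3 subjects: two active, chosen because they are warm, and one vehicle subject chosen because he is not.

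**Conclusion.** The point holds in a limited form. The endpoint makes absence of inflammation part of the definition, the responder analysis omits it, and a local same-visit measure that could flag the problem is not related to net-delta. The plasma panel cannot fill the gap as planned: it has no threshold, no cohort 1 data and none after Day 28, with 60% coverage over Days 7 to 56 and 75% at Day 28.

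The direction of bias favours the drug, on the documents' own attribution of irritancy to the test article. Its size is unknown; the table above rests wholly on an assumed p. A reader might suppose that the bias grows with dose. That is not shown: each injection delivers 5 mg in every cohort by the dose table (40/8 = 80/16 = 120/24 = 180/36 = 5). More injections, and closer spacing in cohort 4, make growth plausible but no more. This is a worthwhile low-cost improvement and does not invalidate the trial.

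**What to change.** In the SAP responder paragraph (second 5.8.4) and Table 14.2.1-3:

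- Keep the row for net-delta of at least 1.
- Add a supportive row, in both arms: net-delta of at least 1 with injected-side Draize erythema 0 and edema 0 at the same visit. The existing row should then be shown for vehicle as well, so that the two can be compared.
- Show net-delta by same-visit injected-side Draize (0 against 1 or more), by arm and cohort, as a subject-level listing where cells are too small.
- State that a warm site with Draize of 1 or more is reported as one where inflammatory heat is not excluded.
- State that Draize 0 does not establish non-inflammatory heat, and is read together with cytokines, MRI and the Day 56 biopsy.

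The cost is SAP wording, one table row and one cross-tabulation, with no new data; whether cohorts 1 and 2 have a Day 56 Draize score should be confirmed. The downsides are very small cells (6 active and 2 vehicle per cohort) and possible loss of true responders with faint erythema, which is why both rows are shown.

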# 2. PURPOSE AND STUDY OBJECTIVES

#### 2.1. PURPOSE

This phase 2a clinical trial aims to test safety and efficacy of a new chemical entity, RZL-012, in converting WAT into a thermogenic tissue and reducing fat-mass in overweight and obese males.

# 2.2. STUDY OBJECTIVES

## 2.2.1. Primary

The primary objective is the evaluation of the overall safety and preliminary efficacy of RZL-012 after subcutaneous injection.

#### 2.2.2. Secondary

The secondary objective is the determination of RZL-012 pharmacodynamics and pharmacokinetics. Evaluation of the existence of a thermogenic effect and the extent, duration and tissue associated changes of the thermogenic response to RZL-012, via minimal invasive means (injected-site thermogenesis, MRI and biopsy) after subcutaneous injection into fatty tissue below the skin.

#### 3. STUDY DESIGN

#### 3.1. DESCRIPTION OF STUDY DESIGN

This is a randomized, double-blind, placebo-controlled, consecutive 4 cohort, dose escalation clinical trial that will enroll 8 subjects, 6 active and 2 control in all cohorts.

#### 3.2. DOSE RATIONALE

The initial dose was determined by the NOAEL established by the GLP extended single dose toxicology study and by the previous phase 0 clinical trial in which 20mg RZL-012 was the highest dose achieved. This initial study is an escalating dose study. If no more than 1 subject experiences intolerable side effects within 14 days following the injection of the last dosed group, according to schedule, an additional cohort of volunteers will be administrated the next dose level.

Cohort 1: 40 mg RZL-012 (1/6.25th of the NOAEL determined in the GLP Toxicology studies).

Cohort 2: 80 mg RZL-012 (1/3.125th of the NOAEL determined in the GLP Toxicology studies).

Cohort 3: 120 mg RZL-012 (1/2.34375th of the NOAEL determined in the GLP Toxicology studies).

Cohort 4: 180 mg RZL-012 (approximately the NOAEL determined in the GLP Toxicology studies).

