If no more than 1 subject experiences intolerable side effects within 14 days following the injection of the last dosed subject according to schedule and following the DSMB approval an additional cohort (Cohort 4) of six volunteers, as above, will receive 36 injections (0.1 mL each in a 9x4 cluster and 1cm apart) adding up to 240 mg RZL-012 (~1/1.39 of the NOAEL).. Additional 2 subjects in the cohort will serve as control and will be injected placebo (vehicle).

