#### 1.2.4. Clinical Studies

Raziel Therapeutics has conducted an Exploratory phase 0, randomized, double-blind, vehicle-controlled study aimed at the evaluation of safety and thermogenesis-induction of three

escalating doses of RZL-012 drug product in overweight and obese volunteers. In each cohort, 8 subjects were enrolled, 6 active and 2 control. Study design is presented in the following table:

Table 1: Phase 0 Clinical Trial Design

	Cohort 1	Cohort 2	Cohort 3
Number of Subjects – Active/Placebo	6/2	6/2	6/2
Total Dose RZL-012 (mg)	5	10	20
Dose per NOAEL*	1/50 th	1/25 th	1/12.5 th
Number of Injections	1	2	4

Primary objective: Evaluation of the overall safety and preliminary efficacy of RZL-012 after subcutaneous injection and the existence of a thermogenic effect.

Secondary objective: Determination of RZL-012 pharmacodynamics and pharmacokinetics. Evaluation of the extent, duration and tissue associated changes of the thermogenic response to RZL-012, via minimal invasive means including injected-site thermogenesis imaging, Magnetic Resonance Imaging (MRI) and punch biopsy following injection into the subcutaneous fat.

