#### 3.3. DOSING

#### 3.3.1. Dosing Regimen

The dosing regimen will be a single dose treatment injection of RZL-012 in multiple sites.

The first 6 subjects randomly assigned to the RZL-012 treatment group (cohort 1) will initiate at the dose of 40 mg RZL-012 (approximately 1/6.25th the NOAEL as determined in the GLP toxicology study) and 2 more subjects will be given placebo (vehicle).

If no more than 1 subject experiences intolerable side effects within the 1st cohort, 14 days following the injection of the last dosed subject, an additional 6 subjects will receive a dose of 80 mg RZL-012 (approximately 1/3.125th of the NOAEL) and 2 more subjects will be given placebo (vehicle).

If no more than 1 subject experiences intolerable side effects within the 2nd cohort, 14 days following the injection of the last dosed subject, an additional 6 subjects will receive a dose of 120 mg RZL-012 (approximately1/2.34th of the NOAEL) and 2 more subjects will be given placebo (vehicle).

If no more than 1 subject experiences intolerable side effects within the 3rd cohort, 14 days following the injection of the last dosed subject, according to schedule an additional cohort of 6 volunteers, as above, will receive 180 mg RZL-012 (1/1.39 of the NOAEL). Additional 2 subjects in the cohort will serve as control and will be injected placebo (vehicle).

Dosing of the first 3 subjects in each cohort will progress consecutively from one individual to the other at 7-day intervals. For additional precaution, the first 3 subjects will be forced randomization with 2 active and 1 control. This study design will allow the physicians to monitor safety in a single subject at each dose; nevertheless, the blindness will remain intact.

The next subjects in the cohort will be randomized to either active treatment or placebo in a ratio determined by the number of subjects targeted for each cohort. Dosing of the next subjects will be in couples and the last subjects will be in a triplet.

If 1 subject had already experienced intolerable side effects in a cohort, then enrollment will progress consecutively from one individual to the other at 7-day intervals until that cohort is complete.

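### The stated NOAEL fraction for cohort 3 (1/2.34) does not fit the reference of about 250 mg that most other dose levels imply, and the cohort 4 dose and fraction also need reconciling

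*Protocol*

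**What the plan says.** Section 3.2 lists the four cohorts with their NOAEL fractions. The figure at issue reads "Cohort 3: 120 mg RZL-012 (1/2.34375th of the NOAEL determined in the GLP Toxicology studies". For the starting dose, the same list has "Cohort 1: 40 mg RZL-012 (1/6.25th of the NOAEL determined in the GLP Toxicology studies", and it puts the 80 mg dose of the second cohort at 1/3.125. The highest dose is described there in words, with no numerical fraction: "Cohort 4: 180 mg RZL-012 (approximately the NOAEL determined in the GLP Toxicology studies".

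The cohort 3 fraction recurs, rounded to 1/2.34, in the synopsis (Study Drug Dosage and Administration, table and text), Section 3.3.1 and Section 6.2.3.1.

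For cohort 4, Section 3.3.1 says subjects "will receive 180 mg RZL-012 (1/1.39 of the NOAEL". The synopsis table and Section 6.2.3.1 agree with that pairing. A later paragraph of the same synopsis section describes the cohort 4 injections as "adding up to 240 mg RZL-012 (~1/1.39 of the NOAEL".

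Table 1 in Section 1.2.4 gives the phase 0 doses as "Total Dose RZL-012 (mg) 5 10 20" and their fractions as "Dose per NOAEL* 1/50 th 1/25 th 1/12.5 th".

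The synopsis and Section 6.2.3.1 give a range of 8 to 48 injection sites. Elsewhere the cohort 4 count is 36 (synopsis table and text, 6.2.3.1, 8.4.2). Section 6.2.3.1 also says that the cohort 2 and cohort 3 injections total 10 mg and 20 mg, although the same paragraphs give the doses as 80 mg and 120 mg.

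**The concern.** Each fraction should be the dose divided by one fixed quantity, the human-equivalent NOAEL. Multiplying any dose by its denominator should therefore return the same number of milligrams. For cohort 3 it does not, and the discrepancy makes the margin look wider than the other dose levels imply. All the sections agree with each other on cohort 3, so comparing them does not reveal it.

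What is at stake is the accuracy of a stated safety figure. Section 6.2.3.1 ties the 120 mg dose to the human equivalent dose from the GLP toxicology study and gives 1/2.34 in the same sentence. For cohort 4 the text leaves open whether the dose is about 72% of the NOAEL or close to all of it, and one paragraph gives a different dose.

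**Working it through.** **Inputs.** Doses and denominators come from the synopsis, Sections 3.2, 3.3.1 and 6.2.3.1, and Table 1 in Section 1.2.4. The implied reference is dose × denominator.

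| Dose level | Dose (mg) | Denominator | Implied reference (mg) |
|---|---|---|---|
| Phase 0, cohort 1 | 5 | 50 | 250 |
| Phase 0, cohort 2 | 10 | 25 | 250 |
| Phase 0, cohort 3 | 20 | 12.5 | 250 |
| Cohort 1 | 40 | 6.25 | 250 |
| Cohort 2 | 80 | 3.125 | 250 |
| Cohort 3 | 120 | 2.34375 | 281.25 |
| Cohort 3, rounded | 120 | 2.34 | 280.8 |
| Cohort 4, most sections | 180 | 1.39 | 250.2 |
| Cohort 4, synopsis paragraph | 240 | 1.39 | 333.6 |

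**Trying to reproduce 2.34.**

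- Common reference: 250 / 120 = 2.083.
- Rounding of 1.39: 180 × 1.385 = 249.3 mg and 180 × 1.395 = 251.1 mg, so 120 mg has a denominator between 2.08 and 2.09.
- Vial strength in Section 8.2: 250 mg / 4.8 mL gives 5.208 mg per 0.1 mL. Then 24 × 5.208 = 125 mg, and 250 / 125 = 2.00.

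None of these gives 2.34. Numerically, 2.34375 = 3.125 × 0.75, whereas a dose step from 80 to 120 mg (×1.5) gives 3.125 / 1.5 = 2.083. That is compatible with an arithmetic slip, but the documents do not say where the figure came from.

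**Size for cohort 3.**

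- Stated: 1 / 2.34375 = 42.7% of the NOAEL.
- On 250 mg: 120 / 250 = 48.0%.
- Overstatement of the margin: 2.34375 / 2.0833 = 1.125, that is 12.5% (2.34 / 2.0833 = 1.123, or 12.3%, with the rounded figure).
- In NOAEL units the step from cohort 2 to 3 reads as 3.125 / 2.34375 = 1.33 and from 3 to 4 as 2.34375 / 1.39 = 1.69. Both dose steps are 1.5 (120 / 80 and 180 / 120).

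**The reverse check.** If 281.25 mg were the intended reference, the denominators would be 281.25 / 40 = 7.03, 281.25 / 80 = 3.52 and 281.25 / 180 = 1.56 for cohorts 1, 2 and 4. None matches what is printed, and the phase 0 fractions would not match either.

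**Cohort 4.** At 1/1.39, the dose is 1 / 1.39 = 72% of the reference. Against 250 mg, 240 mg would be 240 / 250 = 96%. At the 5 mg per injection given for cohort 1 in Section 6.2.3.1, 36 × 5 = 180 mg and 48 × 5 = 240 mg. So the wording in Section 3.2 and the upper limit of 48 sites both fit 240 mg, while 1/1.39 and the count of 36 fit 180 mg.

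**Cohorts 2 and 3 in Section 6.2.3.1.** At 5 mg each, 16 × 5 = 80 mg and 24 × 5 = 120 mg. The printed totals are 10 mg and 20 mg.

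**The case against.** **The fraction drives no decision.** This largely stands. Section 3.2 says the NOAEL and the phase 0 trial determined the initial dose. For later cohorts, Section 6.2.3.1 adds the safety results of the preceding cohort. Escalation requires that no more than one subject has intolerable side effects, together with DSMB review of the safety data to Day 14 (Section 3.3.1). No stopping or eligibility rule uses the fraction, and no analysis in the SAP does. The plan already includes a cohort described as 1/1.39, so moving cohort 3 from 42.7% to 48.0% crosses no threshold in the plan. The doses in mg are printed beside the fractions. A reader might infer that the fraction is the justification for every escalation step. The documents do not support that; it is one part of the stated dose basis.

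**The reference is inferred.** This also stands. The protocol gives animal NOAELs (for pigs, 7.14 mg/kg in males and 6.33 mg/kg in females) but shows no conversion to a human dose in mg. It refers to the Investigator's Brochure for the toxicology detail. The documents can show that the fractions disagree, but not what the true human-equivalent NOAEL is.

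**Approximation might explain the gap.** It does not. Section 3.3.1 does call its fraction approximate, but Section 3.2 prints five decimals without that qualifier, and 12.5% is far beyond rounding.

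**Conclusion.** The point holds as an internal inconsistency. The cohort 3 fraction disagrees with the reference of about 250 mg implied by cohorts 1 and 2, by all three phase 0 doses, and by cohort 4 where it is 180 mg at 1/1.39. On that reference 120 mg is 1/2.08, and the stated margin is about 12.5% too favourable. The size depends on 250 mg being the intended reference.

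Two stronger readings are tempting. The first is that cohort 3 is the only entry out of line. It is not: the synopsis pairing of 240 mg with 1/1.39 implies 333.6 mg, and Section 3.2 describes 180 mg as roughly the NOAEL. The second is that 1/2.08 is the true margin. Without a stated human-equivalent NOAEL, that cannot be established.

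The cohort 4 contradiction is more than two descriptions of one margin, because the dose and the injection count also differ between passages. Nothing here affects sample size, significance level or any planned analysis.

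**What to change.** 1. State the human-equivalent NOAEL in mg once, with its derivation from the animal NOAEL (species, body weight and conversion used).
2. Recompute every NOAEL fraction from that figure: the synopsis table and text, Sections 3.2, 3.3.1 and 6.2.3.1, and Table 1 in Section 1.2.4.
3. Reconcile the cohort 4 dose, fraction and injection count across the synopsis and Sections 3.2, 3.3.1 and 6.2.3.1, including the range of 8 to 48 sites.
4. Reconcile the cohort 2 and cohort 3 injection totals in Section 6.2.3.1 with the doses given there.

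The sponsor must settle which entries stand; this review takes no view on which dose is right. The cost is a text correction in a few places. If 250 mg is confirmed, the stated cohort 3 margin becomes slightly less favourable. If another reference is confirmed, other fractions change instead. The statistical analysis is unaffected.
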